
Figur 1

Hospital/ period	1	2	3	4	5	6
Hospital 1	+suPAR	Control	+suPAR	Control	+suPAR	Control
Hospital 2	Control	+suPAR	Control	+suPAR	Control	+suPAR

Final Protocol (translated from Danish)

**Introducing suPAR measurement in the
emergency departments
(TRIAGE III)**

Technical protocol V.5 (Final)

March 13 2016 /[name]

General information

Steering committee:

Senior researcher, PhD [name], Hvidovre Hospital

Professor, DMSc. [name], Rigshospitalet

Professor, DMSc. [name], Rigshospitalet

M.D., DMSc. [name], Herlev Hospital

M.D., DMSc. [name], Herlev Hospital

Chief Physician [name], Herlev Hospital

Chief Physician [name], Bispebjerg Hospital

Location

The study will take place at Herlev Hospital and Bispebjerg Hospital.

Time plan

Planned start of inclusion is on January 11 2016 and is expected to be concluded on June 6 2016.

Background

Risk assessment is a central concept at admittance of acutely admitted patients to ensure that the sickest patients are treated first and observed the closest. Today, systematized risk assessment is being performed with triage algorithms. According to the primary complaint and vitals sign of the patient an aggregated score is determined by the triage algorithm. Patients are then stratified in groups of acuity that signals how fast they should be assessed by doctors and the frequency of observation¹. In recent years it has been suggested that the risk assessment in the emergency departments can be strengthened by adding results from blood-based biomarkers to the triage process. A combined strategy looks viable both in specific diagnoses²⁻⁴ and in general⁵⁻⁷. However, there is no data to support whether this strategy makes a difference to the patients or which biomarkers that should be used.

Soluble urokinase plasminogen activating receptor (suPAR) is the soluble form of the urokinase-type plasminogen activator receptor (uPAR), which primary is expressed on the surface of cells in the immune system (Neutrophiles cells, activated T-cells and

Inclusion criteria: Acutely admitted patients, who have routine blood-tests (including hemoglobin, C-reactive protein and creatinine) analyzed within six hours of registration. Age of 16 years or above.

Exclusion criteria: Patients admitted in gynecological-/obstetrics-/pediatric regimen.

Measurement of suPAR

Plasma for suPAR measurement will be obtained in connection with routine blood test and will not result in additional discomfort for the patients.

The suPAR level is measured on excess EDTA-plasma from the routine blood tests. The analysis is done with the suPARnostic® Quick Triage stick (QT stick). From routine blood-tests 10 microliter (µl) EDTA-plasma is extracted and transferred to a prefabricated test tube containing 100 µl "running buffer". From the mixture, 60 µl is pipetted to the QT stick which is inserted in the analyzer. The suPAR level is automatically reported on the connected PC after 20 minutes. During the inclusion period it is possible to analyze three tests simultaneously at a minimum of nine tests an hour. When the test result is available it will be reported to the electronic Laboratory system "LABKA" and electronical hospital

records (“OPUS”) as soon as possible and within two hours. Measurement of suPAR is done by study staff, which is present 24 hours every day during inclusion.

Information to attending doctors regarding the suPAR level

Prior to the study period, doctors will receive written information regarding the prognostic value of suPAR in general and with regard to specific diagnoses. In addition, all participating departments will be offered formalized teaching sessions. Doctors will receive a review of the published literature and pocket cards describing risk of 30- and 90-day mortality depending on the suPAR level based on data from Hvidovre Hospital and Hillerød hospital

Data

SuPAR levels as well as all other biochemical test are registered in the LABKA database and can be extracted. Data on all outcomes will be obtained from the central Danish registries.

Power calculation

In a previous unpublished study of patients acutely admitted to the ED at Copenhagen University Hospital North Zealand, Denmark, 12-month mortality was 12.7 % and the frequency of readmissions was 16 % within 5 months.

Our main hypothesis is that we can reduce all-cause mortality to 11.2% by measuring suPAR on admitted patients. Using a 5 % level of significance and a power of 80 %, we will need a sample of 7340 patients in each randomization group to detect this difference an absolute risk reduction in mortality at least 10 months after admission of 1.5 %.

Based upon numbers from the two emergency departments, approximately 170 patients are admitted on a daily basis. During the inclusion period it will be possible to collect data on 10,700 patients in both active- and control periods. This will be sufficient to assess the primary hypothesis.

Ethics and approvals

The study was approved by the board of directors at each participating hospital and department heads of the emergency departments gave consent. The study was presented to the Regional Ethics Committee, who decided that no formal approval was needed in accordance with Danish law (Jr. Nr.: FSP-15003590). All processing of personal data followed national guidelines in accordance with Danish law and the study was approved by the Danish Data Protection Agency (HGH-2015-042, I-Suite nr.04087) and will be registered at the Danish Patient Safety Authority. The study is registered at clinicaltrials.org (NCT02643459).

Economy

Expenses related to the study are financed by ViroGates A / S. Together with ViroGates external funding will be sought for parts of or the entire project.

References


Figure 1:

Hospital/ period	1	2	3	4	5	6
Hospital 1	+suPAR	Control	+suPAR	Control	+suPAR	Control
Hospital 2	Control	+suPAR	Control	+suPAR	Control	+suPAR

Original Statistical analysis plan

The original statistical analysis plan was published with the design article on August 5 2016.

Patients admitted in each intervention or control cycle will be followed as a single cohort and data will be analyzed as randomized. The two groups will be assessed for comparability of the following variables: age, sex, and Charlson score. Differences in mean age of more than 5 years and/or an absolute Charlson Comorbidity Index score of 2 or more will be adjusted for in the final analysis.

Patient data will be analyzed according to which arm of the trial the patient is admitted to during index admission according to the randomization scheme and corresponding to the intention-to-treat principle.

A weighted Cox model will be used to compare mortality at 10 months after inclusion of the last patient. Patients are censored if their first readmission is in the opposite group of their index admission. As this censoring is likely to be dependent censoring (a readmission is rarely a positive prognostic signal), we will employ Inverse Probability of Censoring Weighting (IPCW) where patients readmitted to their own treatment group will be up-weighted to compensate. We will employ stabilized weights such that the reweighted sample has the same implied sample size throughout follow-up. Due to the design, time since index admission is the only covariate that needs to be included in the weights. Reweighting will be done for every two weeks of follow-up. We will not censor nor reweight for 2nd or later readmissions, since the weights would become highly unstable and it is not likely that the presence or absence of an initial suPAR measurement will be important for clinical decisions at this stage.

Furthermore, a traditional intention-to-treat analysis will be performed. Notable difference between the results of the two analysis strategies will be considered critically.

Kaplan-Meier plots will be used to illustrate survival. Unpaired T-test will be used to compare length of stay. $P < 0.05$ will be considered significant.

Subgroup analysis of the following groups will be performed: patients aged 65 year and above, and patients discharged with diagnoses of surgical conditions, cancer, infections, and cardiovascular disease.

Final Statistical analysis plan

April 5 2017

This document contains the statistical analysis plan for the TRIAGE III trial. The statistical analysis plan has been completed prior to the availability of the outcome data. The plan was made available on April 5 2017 on a public website:

<https://www.hvidovrehospital.dk/afdelinger-og-klinikker/Klinisk-Forskningscenter/om-centret/Til-forskere-paa-hospitalet/Documents/TRIAGE%20III%20Analysis%20plan.pdf>
and at clinicaltrials.gov.

Time-line:

Study start: January 11 2016. Study completion: June 6 2016. **The primary analysis will be conducted 10 months after inclusion of the last patient**, which is expected to be April 6 2017.

Background:

The primary research question is: **Can the introduction of a prognostic biomarker strengthen risk stratification of acutely admitted patients leading to fewer deaths.** The study is a cluster randomized controlled interventional trial conducted at two major emergency departments of unselected patients acutely admitted.

Design:

Cluster-randomized, cross-over, parallel interventional two center trial, conducted around six cycles of three weeks in a 1:1 allocation ratio of intervention versus control at each cluster.

Inclusion:

1. ≥ 16 years at admittance.
2. Acute arrival at the emergency department within the inclusion period.
3. Have routine blood tests analyzed, including hemoglobin, C-reactive protein, and creatinine, within 6 hours of admission to the emergency department.

4. As the results of the blood tests can take up to two hours to provide, the doctors cannot change outcome based on biomarker levels until those data are provided. Hence, inclusion time will be calculated as time for blood sampling + 2 hours.

Exclusion:

1. Arrival at the gynecological-, obstetric-, and pediatric department.

Ethics:

The study was presented to the Regional Ethics Committee, who decided that no formal approval was needed in accordance with Danish law. The study has been approved by the Danish Patient Safety Authority (3-3013-1744/1) and data management has been approved by the Danish Data Protection Agency (ID: HGH-2015-042, I-suite: 04087).

Study variables and endpoints:

The following data are collected for the included patients:

- Age
- Results of the routine blood tests at the index admission including suPAR where available. Routine biomarkers: Hemoglobin, Leukocytes, thrombocytes, sodium, potassium, C-reactive protein, Creatinine, ALAT, Albumin, Calcium, lactate. suPAR in intervention periods
- Gender
- Personal Identification number (Danish Civil Registration number (CPR))
- At follow-up (10 months after inclusion of last patient) the following data is collected from the National Patient Registry (NPR)
- Contacts with the hospital system (including all historical contacts)
- Information regarding admissions (date, time and place of admission and discharge)

- Diagnoses (follow-up during study period, historical and in relation to index admission)
- Date of death or immigration (only very few immigrations are expected)
- Charlson score will be calculated using registered diagnoses in NPR dating two years back from index admission

Sample size calculation

In a previous unpublished study of patients acutely admitted to an Emergency Department in Denmark 12-month mortality was 12.7% and readmission rate was 16% within 5 months. Using a 5% level of significance and a power of 80%, the study will need to include 7,340 patients in each group to detect an absolute risk reduction in mortality of 1.5% at 10 months after admission. The two participating hospitals approximately admit 170 patients on a daily basis. During the study period approximately 10,700 patients will be included in every group.

Study end

The follow-up for all patients ends at April 6 2017 and this date will be used as the censoring time for the main analysis.

Statistical plan for main outcome paper

Statistical analyses will be performed using SAS and R.

Consort diagram:

A modified CONSORT trail profile will be used to describe patient flow and total number patients in each group. All patients not included in analysis will be explained.

Baseline description of groups:

Table of summary statistics for each group (described separately for each hospital in appendices) will be presented with a number of baseline variables (age, sex, results of routine blood tests, comorbidities).

Continuous variables will be summarized with: n (non-missing sample size), mean, standard deviation, median, interquartile range, number of missing values. Categorical variables will be reported as frequency and percentages (based on non-missing sample size) and number of missing values.

Continuous and ordinal variables will be tested by Wilcoxon analysis for differences between groups. Categorical variables will be tested with chi-square.

Primary outcome analysis:

The primary outcome will be an **analysis of all-cause mortality between the intervention and control groups**. Patients will be followed as one cohort and data will be analyzed as randomized. Patients will be included at their first contact with the emergency department (index admission) and are followed until the April 6 2017. Any patient lost to follow-up will be censored at the last time known to be alive.

Patients admitted in the intervention period without a suPAR measurement will remain in the intervention group for analyses corresponding to the intention-to-treat principle.

The main analysis of the primary outcome will use a weighted Cox model to compare the primary outcome of all-cause mortality. Patients are artificially censored if they are readmitted at one of the study emergency departments in the opposite group of their index admission. As this censoring is likely to be dependent censoring (a readmission is rarely a positive prognostic signal), we will employ Inverse Probability of Censoring Weighting (IPCW) where patients readmitted to their own treatment group will be up-weighted to compensate. We will employ stabilized weights such that the reweighted sample has the same implied sample size throughout follow-up. Due to the design, time since index admission is the only covariate that needs to be included in the weights. Reweighting will be done for every two weeks of follow-up. We will not censor nor reweight for 2nd or later readmissions, since the weights would become highly unstable and it is not likely that the presence or absence of an initial suPAR measurement will be important for clinical decisions at this stage.

A secondary analysis will be performed where the observational period ends if a patient is readmitted within the inclusion period. We anticipate, that the patients in the secondary analysis will seem healthier and the possible effect of the intervention weaker, although showing the same trend as the main analysis. Notable difference between the results of the main and the secondary analysis strategies will be considered critically.

Finally a per protocol weighted analysis is planned. In this analysis, only patients with a suPAR measurement are included in the intervention group. In order to investigate the difference between these results and the main analysis, we will analyze the mortality differences between patients with and without a suPAR measurement in the intervention periods.

Kaplan-Meier plots will be used to illustrate survival. Robust standard errors will be employed to account for the clustering. $P < 0.05$ will be considered statistically significant

Adjusted analyses of primary endpoint:

Three additional models will also be examined to further examine any role of differences in baseline values of the two groups. The first will include age, sex, CRP and center. The second will further include Charlson score. The third will include all variables used in the descriptive statistics. Results will be presented as hazard ratios with 95% confidence intervals. A forest plot will illustrate the results.

Sensitivity analyses of the primary endpoint:

Sensitivity analyses will be performed: One analysis where all readmissions are censored and a second analysis with only 10 months follow-up for all patients.

Secondary endpoints:

The predefined secondary endpoints of the study are: all-cause mortality at one month of admission; short admission (<24 h) to the emergency department; admission to the medical wards; admission to the intensive care unit; new (not previously registered) cancer diagnosis at the end of the study; length of stay during admission; readmission at one and three months; and economical expenses.

All-cause mortality at one month will be analyzed similar to the primary outcome. The discriminative ability of suPAR with regard to mortality at one and ten months will be assessed by using area under the curve for receiver operating characteristics curves as well as sensitivity, specificity, negative- and positive predictive value. To compare

readmission risk, we will use Cox regression analysis. Cumulative incidence rates adjusted for competing risk (death, readmission) will be estimated. Unpaired t-test will be used to compare length of stay between groups.

Subgroup analyses:

Primary and secondary endpoints (mortality, readmissions, length of stay, discharge from the ED) will be analyzed in the following subgroups according to primary diagnosis at admission: cardiovascular disease, cancer, infections, neurological disease, surgery done during current admission, and patients aged 65 years or older. When Triage data is available, outcomes will be assessed according to DEPT triage categories, as suPAR previously has shown strongest prognostic effect in patients with lowest DEPT triage. All-cause mortality will be analyzed similar to the primary endpoint.

Handling of missing data:

The primary outcome analysis should be subject to no or little missing data as it is based on Danish register data.

Handling of diagnoses for outcome and subgroups:

Diagnoses obtained from the National Patient Registry are coded with the ICD-10 system. The original chapters will be used to group patients according to diagnoses. The primary diagnosis will be used when constructing subgroups and both primary and secondary diagnoses will be used to calculate Charlson score. The following will define the subgroups:

Cancer: Chapter II: Neoplasms (C00-C97 + D37-D48).

Cardiovascular disease: Chapter IX: Diseases of the circulatory system (I09-I52 + I70-I89)

Infections: Chapter I: (A00-B99 + J00-J22 + N10-N11+ N30-N31 + G00-G09)

Neurological disease: Chapter VI: Diseases of the nervous system (G09-G47 + I60-I69)

Surgical conditions: Presence of surgical procedure codes divided into different specialties (general, orthopedic, other)

Summary of changes to the protocol

Changes to the protocol were made before outcome data was available. The final protocol was published as a design article on August 5 2016:

<https://www.ncbi.nlm.nih.gov/pubmed/27491822>

- The study was originally planned to be conducted at three separate hospitals. Due to internal factors and changes in management, Nordsjælland hospital could not continue to participate in the study and withdrew after four days of inclusion. Although attempts were made, it was not possible to find a replacement. Therefore the Steering Committee together with the chief statistician decided to change the study design to a two center model with 1:1 ratio of intervention and control. The new design had three active periods at each center instead of two, which meant that the inclusion period was prolonged until June 6 2016. A new power calculation reflected this change.
- The original follow-up period was planned to be 12 months, but based upon statistical advice the Steering Committee decided to adjust it to 10 months after inclusion of the last patient (median 12 months). It was also decided to include subgroups and adjusted analyses and to reduce the number of secondary endpoints.
- Inclusion- and exclusion-criteria were added.
- The reduction in centers also meant a reduced number of patients eligible for inclusion.

Summary of changes to the Statistical Analysis Plan

Changes to the Statistical Analysis Plan were made before outcome data was available.

- Elaboration of the entire analysis plan.
- Added sensitivity and adjusted analyses of the primary outcome as well as a "per-protocol" analysis.
- Specification of subgroup analyses and definitions of subgroups.

Summary of changes at clinicaltrials.gov:

Changes were made before outcome data was available.

- February 5, 2016: Status of study changed to recruiting. The study started inclusion on January 11, 2016.
- March 1, 2016: The secondary endpoint “Economical expenses” was added after the Steering Committee decided on inclusion of this outcome.
- April 27, 2016: Subgroup analysis was added. Analyses on the following subgroups: Cardiovascular-, infectious-, surgical-, neurological diseases and patients aged older than 65 year. Patients will be eligible for a subgroup based on their primary diagnosis at discharge.
- May 3, 2016: The follow-up period for each patient was changed from 12 months from discharge to one date for all patients, where follow-up ends: 10 months after admission of the last patient: April 6, 2017. This is approximately equal to a median follow-up of 12 months.
- May 31, 2016: Change from 3 to 2 participating centers, which also meant a change in the design, reducing number of control periods to be equal the number of intervention periods. It was clear in the beginning of March that Nordsjælland Hospital had withdrawn from the study. The Steering Committee tried in the subsequent months to find a replacement, which was not possible. The late change on clinicaltrials.gov reflected this.
- June 6, 2016: Status of study changed because of planned stop in the inclusion period.
- April 5, 2017: Original Statistical Analysis plan was made available online.

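### No planned mortality model contains calendar cycle, and the mirrored schedule cancels a shared time trend only if the two hospitals enrol equal numbers

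*Combined protocol and SAP*

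**What the plan says.** The Design section of the Final SAP describes a trial "conducted around six cycles of three weeks in a 1:1 allocation ratio of intervention versus control at each cluster". Figure 1 of the final protocol fixes the order: Hospital 1 has suPAR in cycles 1, 3 and 5, and Hospital 2 in cycles 2, 4 and 6. It does not say which hospital is which. Inclusion runs from January 11 to June 6 2016.

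Entry is once per person: "Patients will be included at their first contact with the emergency department (index admission".

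For the primary outcome: "The main analysis of the primary outcome will use a weighted Cox model to compare the primary outcome of all-cause mortality". No covariates are listed for this model, and its censoring weights depend on time since index admission alone. Of the three adjusted models, "The first will include age, sex, CRP and center". The second adds Charlson score. The third adds the descriptive variables, which are age, sex, routine blood tests and comorbidities. The two sensitivity analyses change the handling of readmissions and the length of follow-up. None of these models contains cycle or calendar date.

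Robust standard errors are promised for clustering, but the clustering unit is not named.

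**The concern.** A cluster cross-over protects against time trends when time is part of the comparison. Two trends are plausible here. One is seasonal, from winter to early summer. The other comes from the plan: because each person enters only once, frequent attenders tend to be taken up in early cycles, and later cycles hold fewer of them.

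At Hospital 1 each suPAR period comes 21 days before its paired control period, and at Hospital 2 it comes 21 days after. A falling mortality trend therefore works against suPAR at one hospital and for it at the other. If one hospital contributes more patients, the two do not offset and part of the trend appears as an arm effect. If the standard error is built from hospital-cycle totals, the trend is also counted as random variation. Both bear on whether a 1.5-point mortality difference can be estimated correctly and detected.

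**Working it through.** **The plan's own figures.** Level and power: "Using a 5% level of significance and a power of 80" per cent. Control risk: "12-month mortality was 12.7" per cent. Effect: "an absolute risk reduction in mortality of 1.5% at 10 months after admission", that is 12.7% against 11.2%. With the two-sided pooled formula,

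n = [1.960·√(2·0.1195·0.8805) + 0.8416·√(0.127·0.873 + 0.112·0.888)]² / 0.015² = (0.8991 + 0.3860)² / 0.000225 ≈ 7,340 per group, as stated.

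Six cycles of 21 days are 126 days, and 170 × 126 / 2 = 10,710 per group, which matches the stated 10,700. The total is 21,420.

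**Assumptions (not in the documents).** Mortality falls linearly across the six cycles at both hospitals, by 2 points (13.5% to 11.5%) or 4 points (14.5% to 10.5%). Hospital 1's share of patients is w. Patients are spread evenly over cycles.

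**Bias.** The mean cycle number is 3w + 4(1−w) = 4−w in the suPAR arm and 4w + 3(1−w) = 3+w in the control arm. The suPAR arm therefore sits 1−2w cycles later. With a fall of d points per cycle, the false risk difference is d(2w−1).

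- w = 0.50: zero for any d.
- w = 0.65, 2-point fall (d = 0.4): 0.4 × 0.30 = 0.12 points, or 8% of 1.5.
- w = 0.65, 4-point fall (d = 0.8): 0.8 × 0.30 = 0.24 points, or 16% of 1.5.

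Simulation of the 12 hospital-cycle cells gave about 0.11 to 0.12 and 0.23 to 0.25 points. The values were the same with center in the model, and essentially zero once cycle was added. If Hospital 2 is the larger, the sign reverses.

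On the hazard scale the leak in the log HR is about (1−2w)b for a slope of b per cycle. If cycle 6 has 0.75 times the hazard of cycle 1, b = ln(0.75)/5 = −0.0575. The spurious HR is then 1.012 at 60:40 and 1.023 at 70:30, against a target HR of 0.875. With patient-level errors, null rejection is 6.3% and 8.8%, falling to 5.1% and 5.0% with cycle.

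**Standard error if clustered on the 12 cells (50:50, 2-point fall).** Each cell holds 21,420/12 = 1,785 patients.

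- Binomial variance per cell: 0.125 × 0.875 / 1,785 = 0.613 points².
- True SD of the difference: √(2 × 0.613/6) = 0.45 points.
- Trend variance over six equally spaced cycles: (35/12) × 0.4² = 0.467 points².
- Expected residual sum of squares per arm: 6 × 0.467 + 5 × 0.613 = 5.87.
- Robust SE with a 12/10 correction: √(2 × 5.87/36 × 1.2) = 0.63; the simulated mean was 0.61.

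For a 4-point fall the simulated SE was 0.96.

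**Behaviour of the remedy under 12-cell clustering (50:50, simulated, corrected SE, t reference).**

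| Model | Residual df | Power, no trend | Power, 2-point fall |
|---|---|---|---|
| Arm only | 10 | 0.86 | 0.61 |
| + hospital + linear cycle | 8 | 0.85 | 0.85 |
| + hospital + categorical cycle | 4 | 0.72 | 0.71 |

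Null rejection is about 5% for both cycle models on the t reference. With categorical cycle it is 11-13% if the corrected SE is read against 1.96, and about 32% if the SE is uncorrected.

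**Precision cost of categorical cycle at 65:35 with no trend.** Per cycle there are 3,570 patients, that is 2,320.5 and 1,249.5. Variance = (1/6) × 0.125 × 0.875 × (1/2,320.5 + 1/1,249.5), so SE = 0.47 points against 0.45 without the terms.

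**Calendar check.** January 11 to June 6 2016 is 147 days, or 7 × 21, against six cycles of 126 days. As an illustration, let both hospitals be in control for one extra period, with equal volumes and hazard falling to 0.75 over seven periods (period hazards sum to 6.090). If the extra period is the first, the spurious HR is [(6.090−1)/6] / [(6.090+1)/8] = 0.957. If it is the third (hazard 0.909), the HR is 0.987. If it is the last, the HR is [(6.090−0.75)/6] / [(6.090+0.75)/8] = 1.041. Direction and size depend on where it falls.

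**Limit.** The simulations used cell proportions or counts. They did not include the censoring weights or the staggered follow-up.

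**The case against.** A reader might infer that any seasonal or depletion trend must contaminate the arm comparison. The documents do not support that. In every cycle of Figure 1 one hospital is on suPAR while the other is control, so each arm covers all six cycles and a shared trend cancels at equal volumes. The hospital split is not given, so the imbalance is a possibility and not a finding. Even at 65:35, a bias of 0.12 to 0.24 points is a quarter to a half of one standard error.

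A reader might also infer that the trial would report a falsely significant result, or that power loss is certain. Neither follows. The inflated standard error arises only if hospital-cycles are the clustering unit, and then it is conservative. With patient-level errors and equal volumes the analysis is unaffected.

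The later adjusted models, with Charlson score, blood tests and comorbidities, may absorb part of the depletion trend. That reduces the concern for those models but not for the main one.

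The strongest objection is to the remedy. Adding categorical cycle while keeping an uncorrected 12-cell sandwich would raise false positives to about a third. This stands, and it is why the error specification has to change together with the model. Cycle terms also do nothing for variation specific to one hospital in one cycle.

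**Conclusion.** The omission is certain, and its consequence is conditional. Bias requires both a shared trend and unequal hospital volumes: zero at 50:50, about 0.1 to 0.25 points at 65:35 for falls of 2 to 4 points, in a direction set by which hospital is larger. Center alone does not remove it. Loss of power requires clustering on hospital-cycles: an SE of about 0.61 against a true SD of about 0.45 for a 2-point fall. Trend sizes and volume splits are assumptions. The unexplained seventh 21-day period adds a separate doubt, because an extra period in one arm would break the mirror even at equal volumes. This should be corrected, but it does not by itself invalidate the design.

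**What to change.** 1. In the main weighted Cox model and the one-month mortality model, stratify the baseline hazard by hospital and add index cycle. Carry both into the three adjusted models. Keep the version without them as a sensitivity analysis.
2. State the clustering unit of the robust standard error in the same paragraph. If it is the hospital-cycle, specify a small-sample correction and a t reference on the residual degrees of freedom. With that unit, prefer a linear cycle term. It held 5% error and about 0.85 power with or without a linear trend, whereas categorical cycle leaves 4 degrees of freedom and about 0.72 power. The linear form does not remove an irregular cycle pattern.
3. Reconcile the 147-day inclusion window with the six cycles, and state each hospital's status in every 21-day period.

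The cost is SAP wording, since place and date of admission are already collected. With categorical cycle, precision is slightly lower if there is no trend and the hospitals differ in size (SE about 0.47 against 0.45 at 65:35). Under hospital-cycle clustering, degrees of freedom come from the 12 cells and not from the number of deaths.
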